3.5 Secondary endpoints

- Documented HIV-1 infection during follow up
- Differences in the PK profile of study products administered 16 weekly (4 monthly) in comparison to 24 weekly (6 monthly) administration
- Differences in the PK profile of study products administered as weight-based dosing in comparison to fixed dosing.
- Changes in the concentration of systemic and mucosal concentrations of CAP256V2LS and VRC07-523LS titres in breakthrough infections
- Proportion of participants reporting CAP256V2LS injections to be acceptable as per study questionnaire

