4.2 Enrollment plan

The study is divided into two parts: **Part A** and **Part B**.

In **Part A (N=90)**, participants will be randomised in a 2:1:2:1 ratio to receive the following: CAP256V2LS 20mg/kg and VRC07- 523LS 20mg/kg administered SC every 16 weeks (4 monthly) or placebo; CAP256V2LS and VRC07-523LS antibodies administered SC every 24 weeks (6 monthly) or placebo (**Table 2**) They will then be followed up and exit the study at Month 12.

In **Part B (N=900)**, participants will be randomised in a 1:1 ratio. Participants will receive an initial fixed dose of 1.2g of CAP256V2LS and 1.2g VRC07-523LS or placebo followed by 600mg of CAP256V2Ls and 1.2g of VRC07-523LS or placebo administered SC every 24 weeks (6 monthly) or placebo. Participants will be followed-up for approximately an average of 18 months with a maximum follow-up of 24 months. Once the last dose is received, participants will be followed up to the next 6 month point to exit the product part of the study and start the 6-month safety and PK follow-up off-product.

All inclusion and exclusion criteria must be met for eligibility to enrol. Enrolment will take place within 56 days of screening. The study accrual period is planned for approximately 10-12 months and eligible participants will receive between approximately 2 to 4 doses in Part B depending the length of time taken to accrue the full cohort.

Safety assessments will be conducted at baseline, following product administration, and at regular intervals as per the Schedule of Evaluations (SOE). PK assessments will be conducted retrospectively on stored samples for all HIV seroconvertors and a sub-set of participants at a minimum of two timepoints. HIV testing will be conducted as per the SOE.

Table 2: CAPRISA 012C dosing table

Part A

Group	Participants	Regimen*	N= 90	Dose (mg/kg)
1a	HIV negative	CAP256V2LS + VRC07-523LS	30	20 mg/kg SC + 20 mg/kg SC at 16-week (4 monthly) dosing intervals
1b	HIV negative	CAP256V2LS + VRC07-523LS	30	20 mg/kg SC + 20 mg/kg SC at 24-week (6 monthly) dosing intervals
1c	HIV negative	Placebo	30 (15 each)	Normal saline SC at 16 or 24-week (4 or 6 monthly) dosing intervals

*Study products will be administered as two separate injections with or without hyaluronidase.

Part B

Group	Participants	Regimen*	N=900	Dose (mg/kg)

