Table 5 shows the two-sided exact 95% confidence interval for the observed true event rate. If one or two of the 450 participants receiving CAP256V2LS and VRC07-523LS experiences a safety event, the upper bound of the two-sided 95% confidence interval will be 1.25% or 1.61%, respectively. If 20 or 40 participants experienced an event, these estimates of 4.4% and 8.9% will be compatible with plausible event rates from 2.90% to 6.76% and 6.60% to 11.88%, respectively.

Table 6: Two-sided 95% confidence intervals based on observing a particular rate of safety endpoints

Number of events/ sample size	95% confidence interval
0/450	0 – 0.85
1/450	0.04 – 1.25
2/450	0.12 - 1.61
10/450	1.21 – 4.04
20/450	2.90 – 6.76
40/450	6.60 – 11.88

Since this extended safety study is being undertaken in the populations where a phase III trial would be conducted, it is expected to generate a preliminary estimate of efficacy. The statistical power to demonstrate 67% efficacy is 82% if the background incidence rate in the phase II trial is 4 per 100 person-years and 90% if the HIV incidence rate is 5 per 100 person-years. The rationale for using the background HIV incidence rate ranging from 3 to 5 per 100 person-years, is that the HIV incidence rate in the placebo arm of the AMP, ASPIRE and RING study were 2.98, 4.5 and 6.1 per 100 women-years, respectively. The calculations in **Table 7** allows for a lower HIV incidence in Zambia. Power calculations were based on an exponential maximum likelihood test of equality of survival curves from nQuery (2021) (Statistical Solutions Ltd), Cork, Ireland.

Table 7: Power and HIV endpoints for varying effectiveness and background incidence rate

Statistical power for background HIV incidence rates when the sample size is 900; accrual of 9-12 months and maximum follow-up of 24 months				
Incidence	67% effectiveness		80% effectiveness	
	HIV events	Power	HIV events	Power
2	13	53%	9	67%
3	20	70%	13	84%
4	27	82%	18	93%

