The MITT population will be used for this analysis. However, sensitivity analyses may be performed, limited to participants who received a certain number of doses or an analysis comparing each of the intervention arms to all placebo receiving participants, may be performed. The date of HIV infection diagnosis will be estimated as the midpoint between the last negative HIV test and the first confirmed positive HIV test date. Where a participant has a positive PCR and a negative or discordant rapid results on the same date, the date of infection is calculated as 14 days prior to this date. Alternatively, the single random-point method will be used in instances where we have missed visits(43). Participants who do not become HIV positive before their last study visit will be censored on the day of their last negative HIV test. Time at risk in days will be computed as the difference between the estimated date of HIV infection or date of censoring and the randomization date. The hazard ratio comparing CAP256V2LS + VRC07-523.LS vs placebo and a 95% confidence interval will be estimated using the univariable Cox proportional hazards model. Product efficacy calculated as 1 minus the hazard ratio and a 95% confidence interval will be presented. Secondly, Cox proportional hazards regression models will be used to estimate the hazard rate ratio and product efficacy along with a 95% confidence interval, controlling for baseline prognostic variables to improve precision.

In the event where the proportional hazards assumption is violated, a Poisson model with person-years of follow-up as an offset will be utilised. Furthermore, a sensitivity analyses will be conducted where the counterfactual placebo HIV incidence rate will be compared with the HIV incidence rate among those receiving CAP256V2LS and VRC07-523LS antibodies.

Acceptability of the SC injections among participants

The number and percentage of participants who discontinue the study product or prematurely withdraw from the study will be reported by study arm, with reasons for discontinuation summarised.

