- 3.Includes pre-test counseling and post-test counseling as indicated. A subsequent follow-up contact may be conducted to provide post-test counseling and to report results to participant.
4. Conducted when clinically indicated
- 5.Reactogenicity assessments performed at approximately 60 minutes post study product administration and via virtual visit three days post study product administration as per protocol. If required this information will be updated on the DAY 7 virtual visit.
- 6.Total blood volume collection will not exceed 500 mls within 6 weeks
- 7.May include urine or serum pregnancy test as clinically indicated
- 8.HIV testing will be conducted as per an HIV testing algorithm described in the SSP
- 9.PK assessments will be conducted retrospectively on stored samples for all HIV seroconvertors and a sub-set of participants at a minimum of two timepoints
- 10.Genital mucosal sampling will include ~~eyebushes~~, genital swab/s and/or Softcup.

#Once the last dose is received, participants will be followed up to the next 6 month point to exit the product part of the study and start the 6-month safety and PK follow-up off-product

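### The Part B HIV efficacy analysis has no cut at product exit, so it takes in the planned 6-month off-product period that Table 7's 24-month horizon leaves out

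*Protocol*

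**What the plan says.** On the analysis, section 9.4.2 (HIV infections) states: "The MITT population will be used for this analysis". Time at risk runs from randomisation to the estimated infection date or to censoring, and the censoring rule is "Participants who do not become HIV positive before their last study visit will be censored on the day of their last negative HIV test". The estimator is a Cox model: "Product efficacy calculated as 1 minus the hazard ratio and a 95% confidence interval will be presented". The optional sensitivity analyses compare arms or are "limited to participants who received a certain number of doses"; none is restricted by time since the last dose. The endpoint in section 3.5 is "Documented HIV-1 infection during follow up".

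On the duration of Part B, section 4.2 says: "Participants will be followed-up for approximately an average of 18 months with a maximum follow-up of 24 months". It plans about 2 to 4 doses at 24-week intervals. It and the footnote to Appendix 3 then say that, at the 6-month point after the last dose, women "exit the product part of the study and start the 6-month safety and PK follow-up off-product". Appendix 3 places the last dose at M18 (week 72) and runs to M30. Table 7 in section 9.2 is headed with "accrual of 9-12 months and maximum follow-up of 24 months". The study schema in section 1.0 gives yet another set of lengths, about 16, 18 or 20 months.

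**The concern.** The stopping rule is tied to the last HIV test, and HIV testing continues after product exit. Months 6 to 12 after the last dose therefore count as antibody-arm time at risk, and infections in that window count against the product. If protection falls after the dosing interval, the result labelled product efficacy averages a protected and a less protected period. The off-product share also differs between women: 6 of 18 months (one-third) after two doses, and 6 of 30 months (one-fifth) after four.

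Section 3.1 makes an efficacy estimate part of the trial's aim, and section 2.3 uses breakthrough infections to guide the phase III dose and interval. A diluted estimate would feed into both. The analysis would also cover a different period from the one on which its power was calculated.

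**Working it through.** **Does HIV testing reach the off-product period?** The Appendix 3 table is broken in the available text, but its HIV-testing row carries 11 marks. Only 10 clinic visits run from screening to M24 (SCR, M0, M3, M6, M9, M12, M15, M18, M21, M24). At least one test therefore falls after M24. The row also ends in the same column as the exit PBMC sample.

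**Which period does Table 7 cover?** Inputs from section 9.2: 450 per arm, hazard ratio 0.33, exponential maximum-likelihood test, accrual up to 12 months. Assumptions: uniform accrual, two-sided alpha 0.05 (stated only for the safety calculation), and dropout of 10% per year (10% is stated without a time scale).

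| Incidence per 100 PY | Stated power | 24-month horizon | 30-month horizon |
|---|---|---|---|
| 2 | 53% | 53.2% | 64% |
| 3 | 70% | 70.2% | 81% |
| 4 | 82% | 81.8% | 90% |
| 5 (text) | 90% | 89.2% | 95% |

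The 67% column matches a 24-month horizon and not a 30-month one, so it leaves out the off-product months. Uniform accrual over 12 months with a 24-month maximum also gives the 18-month average in section 4.2. Two side observations do not affect this point. The 80% column does not reproduce with these settings (73%, 88%, 95% against 67%, 84%, 93%). Table 7's 27 events at 4 per 100 PY are the number required for 82% power, not the roughly 32 to 35 expected from the stated follow-up.

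**How large is the dilution?** Let r be the off-product efficacy, which the documents do not give. With 18 months on product and 6 off, the person-time-weighted hazard ratio is

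HR = [0.33 × 18 + (1 − r) × 6] / 24.

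- r = 0: (5.94 + 6.00)/24 = 0.498, efficacy 50%
- r = 33.5% (one-third): (5.94 + 3.99)/24 = 0.414, efficacy 59%
- r = 50% (one-half): (5.94 + 3.00)/24 = 0.373, efficacy 63%
- r = 67% (no waning): 0.33, efficacy 67%

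If the 18-month average already includes the off-product months (12 on, 6 off), r = 0 gives (3.96 + 6.00)/18 = 0.553, efficacy 45%. The r = 33.5% and r = 50% cases give 56% and 61%.

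**What happens to power at 4 per 100 PY?** Without dropout, placebo events over 24 months are 450 × 0.04 × 2 = 36.0. Antibody events are 450 × 0.04 × [1.5 × 0.33 + 0.5 × (1 − r)]. Then z = |ln HR| / √(1/36.0 + 1/antibody events), and power = Φ(z − 1.96).

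| Analysis | Antibody events | z | Power, formula | Power, simulated Cox |
|---|---|---|---|---|
| Product phase only (27.0 placebo events) | 8.9 | 2.87 | 82% | 84% |
| Full follow-up, r = 0 | 17.9 | 2.41 | 68% | 66% |
| Full follow-up, r = 33.5% | 14.9 | 2.86 | 82% | 82% |
| Full follow-up, r = 50% | 13.4 | 3.09 | 87% | 87% |

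The simulation used product phases of 12, 18 or 24 months plus 6 months off. Its median efficacies were 51%, 59% and 64% for the three full follow-up rows.

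**The case against.** A reader might infer that the trial will report about 50% efficacy in place of 67% and that its power falls from 82% to 68%. The documents do not support that as a statement of fact. Both figures need 67% efficacy up to product exit and none from the next day, and no section gives protection for months 6 to 12 after the last dose. The 33-day subcutaneous half-life in section 2.6.2 implies that 2.9% of the antibody remains at 24 weeks and 0.1% at 48 weeks. But that half-life is for VRC07-523LS alone; the protocol gives no human half-life for CAP256V2LS. Section 2.3 says no protective concentration is known in humans. Waning is plausible, but its extent is open, and the power loss disappears by about one-third residual protection.

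It is also fair to say that analysing all follow-up is not an error in itself. It preserves the randomised comparison, and waning only biases it toward no effect. Efficacy is secondary, and the off-product months are described as safety and PK follow-up, so an author may have meant to keep them apart.

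Three replies stand:
- Section 9.4.2 states the time-at-risk rule outright and treats departures in the SAP as deviations, so this is not a detail merely left to the SAP.
- The dose-number restriction selects women, not time: a woman with every dose still contributes her off-product months.
- The Poisson fallback for non-proportional hazards uses a person-years offset, so it returns the same time-averaged ratio as the formula above. The counterfactual comparison states no cut either.

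**Conclusion.** The point holds as a badly fixed analysis window. As written, the HIV analysis includes the planned off-product period, while section 4.2 and Table 7 rest on a 24-month maximum without it. That mismatch stands whatever the residual protection is.

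The size of any bias is conditional. Under 18 months on and 6 off, estimated efficacy runs from about 50% (zero residual) through 59% (one-third) to 63% (one-half), against a true on-product 67%. It could be 45% at zero residual if the 18-month average already includes the off-product months. Power at 4 per 100 PY is about 66–68% at zero residual and about 82% or higher from one-third upward.

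This should be fixed. It is not critical, because the primary safety endpoints are unaffected and efficacy is a secondary objective.

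**What to change.** In section 9.4.2, define the main Part B HIV analysis as running from randomisation to the scheduled product-exit visit, that is, the 6-month point after the last scheduled dose. Apply the cut identically in both arms, by schedule and regardless of missed doses. Censor uninfected women at their last negative test on or before that visit. State how a woman is handled who misses the exit-visit test and later tests positive, since her estimated infection date could fall on either side of the cut.

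Report off-product infections by arm as a separate period, and keep full follow-up as a sensitivity analysis. Reconcile the follow-up lengths in section 1.0, section 4.2, Table 7 and Appendix 3, separating the product phase from the off-product phase.

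The cost is a few sentences. Off-product events leave the main count, which would lower power if residual protection is substantial, but they remain reported. The randomised comparison is kept, and the analysis then matches its own power basis.

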9.3 Randomisation and arm allocation

In part A, participants will be randomised in a 2:1:2:1 ratio to receive the following: CAP256V2LS and VRC07- 523LS antibodies administered SC every 16 weeks or placebo; CAP256V2LS and VRC07- 523LS antibodies administered SC every 24 weeks or placebo. Whereas in part B, participants will be randomised in a 1:1 ratio to receive a fixed dose of CAP256V2LS and VRC07- 523LS antibodies administered SC every 24 weeks (6 monthly) or placebo.

Participants and study staff (except for study pharmacists) will be blinded as to participant treatment and initially will also be blinded to treatment schedule (where applicable). The randomization list containing, unique sequential treatment codes, will be generated by an unblinded study statistician and will be used to assign individual study participants to one of the two study arms within a 4- and 6-monthly dosing schedule. The randomization list will be obtained by computer generated random numbers, where a randomly permuted block design, stratified by research site, will be used. The site study pharmacist at each research site is responsible for secure storage of this list. A separate blinded list consisting only of the blinded treatment code, in sequential order, will be provided to the study clinic. Alternatively, this blinded list will be provided through DFdiscover system.

All the unblinding decisions will be made by the principal investigator, where possible, after consultation with the DSMB or the PSRT.

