9.4.2 Data analyses

Analyses for primary endpoint(s) and some of the secondary endpoints will be performed using SAS version 9.4 or above (Statistical Analysis Software, North Carolina, USA) and or R statistical software. MITT analyses will be used for the analyses of safety endpoints. Inferential statistical analyses will be performed with all participants receiving CAP256V2LS and VRC07-523LS antibodies irrespective of the dosing frequency (in Part A) grouped and compared to all the participants receiving placebo. Sensitivity analyses may be performed where the intervention arm will be compared to the placebo arm within each dosing frequency (in Part A).

All deviations to be made to the statistical considerations in this protocol will be documented in the detailed statistical analyses plan (SAP) together with a detailed analysis plan for secondary objectives.

Participant demographics

Demographic data of all participants enrolled in the study will be summarized using descriptive statistics. No inferential statistics will be performed to compare demographics and any other baseline variables by study arm.

Reactogenicity

The number and percentage of participants experiencing each type of reactogenicity sign or symptom will be tabulated by severity and study arm. Each participant's reactogenicity sign or symptom will be counted once under the maximum severity for each injection. In the combined intervention and controls arms, the number and proportion of participants experiencing at least one grade 3 or higher local or systemic reactogenicity signs and symptoms across all injection visits will be compared using Fisher's exact test.

Adverse events and serious adverse events

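### The main HIV Cox model omits the site stratum, and the safety test can be read as pooling Parts A (2:1) and B (1:1) without a part stratum: small effect, free to fix

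*Protocol*

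**What the plan says.** **Randomisation.** Protocol section 9.3 describes computer-generated lists "where a randomly permuted block design, stratified by research site, will be used". The two parts have different allocation: "In part A, participants will be randomised in a 2:1:2:1 ratio", which is 60 antibody to 30 placebo (Table 2), and "Whereas in part B, participants will be randomised in a 1:1 ratio", which is 450 to 450.

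**Site and HIV risk.** Section 9.2 says that Table 7 "allows for a lower HIV incidence in Zambia". Section 4.1 puts up to 25% of participants in Zambia.

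**HIV analysis.** In section 9.4.2 the hazard ratio and its confidence interval "will be estimated using the univariable Cox proportional hazards model". A second Cox model follows, "controlling for baseline prognostic variables to improve precision"; it names neither site nor part. The subsection is said to concern mainly Part B, but Part A is not excluded. As an optional sensitivity analysis, "an analysis comparing each of the intervention arms to all placebo receiving participants, may be performed".

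**Safety analysis.** Section 9.4.2 takes antibody recipients "irrespective of the dosing frequency (in Part A) grouped and compared to all the participants receiving placebo". The reactogenicity endpoint is then tested between the combined arms with Fisher's exact test. No stratum is mentioned.

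**The concern.** Site is a design stratum and, by the protocol's own account, prognostic for HIV. The usual practice is to carry such a factor into the main model. Here the headline efficacy estimate leaves it out, and the adjusted model does not guarantee that it comes in.

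The second issue is the safety comparison. If all means both parts, antibody recipients are 67% of Part A and 50% of Part B. The parts differ in dosing, in number of doses (two or three in Part A, about two to four in Part B) and in assumed event rates; section 9.2 expects fewer severe reactions with the fixed dose. A crude comparison then mixes part with arm, so some difference can appear with no product effect. This touches a primary endpoint. It would also mean that the comparison analysed is not the one that was sized.

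**Working it through.** **1. The plan's own figures**

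- Part B safety sample size (section 9.2: 4.8% vs 1%, two-sided 0.05, 90% power). Normal approximation without continuity correction: n = [1.960·√(2·0.029·0.971) + 1.282·√(0.048·0.952 + 0.01·0.99)]² / 0.038² ≈ 408 per arm. Allowing for 10% dropout, 408/0.9 ≈ 454, against 450 stated. Exact Fisher power with 405 per arm (450 less 10%) is 89.8%.
- HIV power (Table 7: 27 events, 67% efficacy, incidence 4 per 100 person-years). √(27/4)·|ln 0.33| − 1.960 = 2.880 − 1.960 = 0.920, so power is 82.1%, against 82% stated.

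Both reproduce. Both concern Part B alone, as do Tables 5 and 6 (450 antibody recipients).

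**2. Leaving site out of the Cox model**

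The protocol does not say how much lower incidence is in Zambia, so the site incidences below are assumptions (two South African sites, then Zambia; per 100 person-years). Simulated results for Part B, 3,000 trials per scenario:

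| Site incidences | Null rejection: unstratified / by site | Power at HR 0.33: unstratified / by site |
|---|---|---|
| 4, 4, 4 | 5.3% / 5.3% | 84.5% / 84.6% |
| 5, 5, 1 | 5.0% / 5.1% | 85.3% / 85.5% |
| 6, 3, 1.5 | 4.8% / 4.8% | 82.5% / 82.9% |
| 4.5, 4.5, 2 | 4.6% / 4.6% | 84.2% / 84.3% |

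The standard error of the log hazard ratio is the same both ways to three decimals (for example 0.405 and 0.405), and the median hazard ratios agree within 0.002 at HR 0.33. The simulated trials have 31 to 33 events, more than Table 7's 27, so only the difference within each row matters. With Part A added and strata formed by site and part, power again differs by less than 0.5 point. A separate run of 1,200 trials at incidence 5 in South Africa and 1 in Zambia gave 84.8% and 85.3%.

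**3. Pooling the parts for safety, no product effect**

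With event rate a in Part A and b in Part B, the same in both arms:

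Crude RR = [(60a + 450b)/510] / [(30a + 450b)/480]

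- a = 1.5%, b = 1% (the upper Part A placebo rate in section 9.1 and the Part B rate in section 9.2): 1.059% / 1.031% = 1.03
- a = 3%, b = 1% (Part A rate assumed): 1.235% / 1.125% = 1.10
- a = 6%, b = 1% (Part A rate assumed): 1.588% / 1.3125% = 1.21

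Type I error at nominal 5%, 40,000 simulated trials each:

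| Rate A / rate B | Pooled Fisher | Cochran-Mantel-Haenszel by part |
|---|---|---|
| 1% / 1% | 3.1% | 4.7% |
| 3% / 1% | 3.4% | 4.7% |
| 6% / 1% | 4.6% | 4.8% |
| 10% / 2% | 5.7% | 4.9% |
| 20% / 2% (extreme) | 10.3% | 5.1% |

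**4. Pooling the parts for safety, at the planning rates**

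With antibody/placebo rates of 6%/1.5% in Part A and 4.8%/1% in Part B:

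- Crude RR = [(3.6 + 21.6)/510] / [(0.45 + 4.5)/480] = 4.941% / 1.031% = 4.79
- Mantel-Haenszel RR = (3.6·30/90 + 21.6·450/900) / (0.45·60/90 + 4.5·450/900) = 12.0/2.55 = 4.71
- Power: 96.5% for pooled Fisher, 96.6% for the part-stratified test, 93.1% for Fisher in Part B alone (all without dropout)

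**The case against.** **The safety sentence may concern Part A only.** Its bracket refers to dosing frequency in Part A, and the sensitivity analysis after it is also within Part A frequencies. Merging those two frequencies is sound, because both are 2:1. The sizing and Tables 5 and 6 treat Part B alone. This objection stands in part. Pooling across parts is the literal reading, but the protocol never states it outright, so a reader who concludes that the parts will certainly be combined goes beyond the text. Equally, nothing limits the sentence to one part.

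**The adjusted Cox model could include site, and details of secondary analyses are left to the SAP.** That is fair. But section 9.4.2 already fixes the unadjusted model as the first estimate and treats the SAP as the place to record deviations. The adjusted model does not secure the site term.

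**There is no demonstrated harm from omitting site.** This stands. A reader might infer that ignoring the stratum gives a wrong standard error or a miscalibrated test. The simulations do not support that: standard error, type I error and power are practically the same both ways.

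**For HIV, the part issue is nearly moot.** This also stands. The analysis is mainly Part B, and the comparison with all placebo women is optional. Its reference to several intervention arms does bring Part A into scope, since Part B has only one antibody arm; set against all placebo women, a Part A arm would be partly compared with women who were not randomised alongside it.

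**The larger relative risks need rates above those planned.** Correct: at the protocol's own placebo rates the figure is 1.03.

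**Conclusion.** The point holds as a minor one. The main HIV model omits a randomisation stratum that the protocol itself treats as prognostic, and the safety text leaves open a crude comparison across two parts with different allocation ratios.

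The gain from stratifying by site is consistency with the design; the change in power is at most about 0.5 point. The distortion from pooling is 3% on the relative-risk scale at the protocol's placebo rates, and 10% to 21% if Part A rates were 3% to 6%. Pooled Fisher type I error passed 5% only in the 10%/2% and 20%/2% scenarios, far above the planned placebo rates. These results rest on assumed site incidences and assumed Part A null rates, shown as ranges. It would be wrong to infer that the trial is undersized: no stated sample size or power changes.

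**What to change.** In section 9.4.2, or in the SAP as a documented deviation from it:

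1. Make the main HIV model a Cox model stratified by research site, in Part B. Keep the univariable model as a sensitivity analysis if wanted.
2. State whether Parts A and B are combined for safety. Preferably make Part B alone the main reactogenicity comparison, since that is the one that was sized. If the parts are combined, use an exact or Mantel-Haenszel test stratified by part (and site).
3. In the optional sensitivity analysis, compare each antibody arm only with the placebo group of its own part.

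The cost is wording only: no extra data, participants or visits.
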